**Table 1.3.2A** **IM101063 Treatment Groups Based on Body Weight**

Treatment Group	Subject weight (kg)	IV dose on Day 1 (mg)	SC dose weekly for 12 weeks (mg)	SC injection volume (mL)
1	< 60	500	75	0.6
2	< 60	500	125	1
3	60 - 100	750	125	1
4	> 100	1000	125	1
5	> 100	1000	200	0.6 + 1.0

Source: IM101063 CSR

On Day 1, subjects received a single IV infusion (loading dose) of abatacept or placebo, based on their weight range. Approximately 1 hour after the completion of the IV infusion, subjects received their assigned SC dose of abatacept or placebo. Abatacept or placebo was administered weekly by the SC route, at the same dose as the SC dose on Day 1, for a total of 12 SC injections. Blood samples for PK analysis were collected on Day 1 prior to and at the end of the IV infusion. In addition, blood samples were collected prior to each weekly SC dose of abatacept.

Steady-state trough serum concentrations were achieved after ~ 4 to 5 weeks following the combined regimen of a single IV loading dose and weekly SC injections. With the exception of Treatment group 4 (abatacept 125 mg SC weekly dose for subjects weighing > 100 kg), the mean steady-state trough concentrations across all other treatment groups appeared to be comparable.

However, to truly represent the steady-state serum levels from SC administration without the contribution of the IV loading dose, Cmin values on Days 71-85 were selected, since contribution from IV was expected to be negligible. Comparison of mean steady-state trough concentrations on Day 71, 78 and 85 indicated that abatacept did not appear to accumulate following weekly dosing (Table 1.3.2B).

**Table 1.3.2B:** **Summary Statistics for Abatacept Steady-State Cmin Values on Days 71, 78, and 85 - IM101063**

Treatment Group	Study Day	n	Cmin ( $\mu$ g/mL) Geometric Mean (CV%)	Cmin ( $\mu$ g/mL) Median (Min, Max)
1 (500 mg IV / 75 mg SC)	71	7	22.64 (20.13)	20.92 (17.06, 29.84)
	78	7	21.66 (19.99)	22.40 (16.01, 28.93)
	85	7	23.62 (31.63)	21.91 (18.24, 39.60)

**Table 1.3.2B: Summary Statistics for Abatacept Steady-State Cmin Values on Days 71, 78, and 85 - IM101063**

Treatment Group	Study Day	n	Cmin ( $\mu\text{g/mL}$ ) Geometric Mean (CV%)	Cmin ( $\mu\text{g/mL}$ ) Median (Min, Max)
2 (500 mg IV / 125 mg SC)	71	4	28.03 (42.13)	32.57 (13.73, 43.30)
	78	3	34.17 (29.49)	33.10 (25.97, 46.40)
	85	3	36.73 (31.64)	37.50 (26.26, 50.30)
3 (750 mg IV / 125 mg SC)	71	26	24.05 (40.65)	26.53 (7.97, 54.11)
	78	23	24.41 (52.35)	27.54 (5.40, 68.90)
	85	25	24.93 (38.42)	26.01 (9.57, 53.80)
4 (1000 mg IV / 125 mg SC)	71	3	16.22 (24.39)	15.15 (13.37, 21.07)
	78	5	11.57 (32.25)	13.20 (6.89, 16.33)
	85	5	13.01 (41.35)	13.30 (6.66, 22.73)
5 (1000 mg IV / 200 mg SC)	71	5	26.52 (56.53)	26.20 (8.68, 55.20)
	78	5	29.21 (52.96)	40.40 (8.04, 57.10)
	85	5	27.53 (58.87)	29.01 (8.74, 62.00)

Source: IM101063 CSR, Supplemental Table S.8.2.2

n=number of observations

Steady-state pharmacokinetic parameters of abatacept after weekly SC administration were determined between the SC dosing interval from Day 71 to 78. Cmax and AUC(TAU) appear to be comparable in Treatment Groups 1, 3 and 5 (Table 1.3.2C).

**Table 1.3.2C      Summary Statistics for Abatacept Steady-State Pharmacokinetic Parameters - IM101063**

Treatment Group	Pharmacokinetic Parameter	
	Cmax (µg/mL) Geometric Mean (CV%)	AUC(TAU) (µg*h/mL) Geometric Mean (CV%)
1 (500mg IV / 75mg SC)	n = 7 26.3 (29.5)	n = 7 4066 (22.2)
2 (500mg IV / 125mg SC)	n = 4 34.9 (46.6)	n = 3 6699 (20.7)
3 (750mg IV / 125mg SC)	n = 26 31.9 (42.8)	n = 24 4607 (38.6)
4 (1000mg IV / 125mg SC)	n = 5 14.7 (44.3)	n = 4 2555 (30.1)
5 (1000mg IV / 200mg SC)	n = 5 41.7 (41.2)	n = 5 5849 (40.5)

Source: IM101063 CSR, Supplemental Table S.8.2.3

n = number of subjects, TAU = 7 days

Cmax and AUC(TAU) were calculated between a SC dosing interval from Day 71 to Day 78 profile.

### **SC formulation in pediatric population**

Data are not available for clinical pharmacokinetic parameters of SC abatacept in children.

#### **1.3.3      Safety of Abatacept in Core Rheumatoid Arthritis Studies**

The clinical safety data for abatacept (IV formulation) in subjects with RA is derived from:

- the open-label, long term (LT) periods of the 5 core RA studies, plus LT data from 3 supportive studies (IM101043, IM101064, and IM101015) and ST and LT data from IM101023
- the double-blind period of the JIA study (IM101033)
- the post marketing experience with abatacept and
- the data collected for post-marketing commitments to regulatory authorities.

The safety data from the open label LT periods of the clinical studies were analyzed in 2 ways; one to assess the LT safety profile of abatacept (Integrated Population) and another to assess the safety profile of abatacept across 3 prior therapy populations (Prior Therapy Population). Collectively, the Integrated Population safety experience covers the LT periods of the RA clinical studies from the methotrexate inadequate-responders (MTX-IR) and tumor necrosis factor inadequate responders TNF-IR studies, which includes up to 8 years of continued exposure (11,658 person-years [p-y] experience with 1030 subjects with at least 5 years of exposure); new data from an earlier population of MTX-naïve subjects followed for 2 years including assessments at 1 and 2

years; as well as data from pharmacovigilance monitoring under the conditions of market usage (~32,187 p-y experience). For the Prior Therapy Population, there were 4,632 subjects (12,375 p-y) treated with abatacept in combination with MTX,

- 1,280 MTX-IR subjects, representing 4,465 p-y of exposure, who were treated for up to total of 8 years; and
- 1419 TNF-IR subjects, representing 1,986 p-y of exposure, who were treated for up to total of 5.5 years;

The remaining 483 MTX-naive subjects represented 717 p-y of exposure and were treated with abatacept for up to 2 years .

#### **1.3.4 Safety of SC Formulation**

##### **SC formulation in adult population**

###### **IM101013**

In Study IM101013, a double-blind, randomized (within dose), placebo-controlled, parallel-group, single-dose study in healthy subjects weighing  $\leq 100$  kg, single SC doses of abatacept were well-tolerated by healthy adult subjects. There were no deaths, no discontinuations, and no SAEs reported. All AEs were mild to moderate in intensity. In general, there was no difference between the frequency and types of AEs reported by the abatacept (all abatacept groups combined, n = 40) and placebo (all placebo groups combined, n = 8) groups. The most common type of AEs reported by abatacept and placebo subjects were injection site reactions including erythema, swelling, and tenderness. Infections were commonly reported by both the abatacept and placebo groups and were not more common in abatacept-treated subjects than in placebo-treated subjects. One (1) abatacept-treated subject had laboratory abnormalities (increases in alanine aminotransferase and gamma-glutamyl transferase levels) that were considered by the investigator to be clinically significant and were reported as AEs.

Overall, 11 of the 40 subjects (27.5%) developed antibodies to the CTLA4 region of the abatacept molecule, with endpoint titers in healthy subjects followed for 71 days ranging from Day 33 to Day 872. Only 1 of the 11 subjects developed antibodies that had abatacept neutralization activity. The earliest onset of seroconversion was at Day 43 (seen in 1 subject), after approximately 3 to 4 half-lives of abatacept and accounting for over 94% of the drug being eliminated from the vascular system. The presence of an immune response resulted in increased clearance of abatacept from the vascular system. This resulted in a shorter  $T_{1/2}$  (range = 3.2 to 7.5 days) compared with the  $T_{1/2}$  for subjects who did not exhibit an immune response to abatacept (range = 11.2 to 14.7 days). The incidence rate of seroconversion in subjects receiving a single SC dose of abatacept (27.5%) was higher compared with subjects who discontinued IV abatacept treatment (7.4%) in the Phase 2/3 development program of IV abatacept for RA. The development of immunogenicity did not appear to be associated with adverse safety outcomes; the safety profile of abatacept in subjects with and without an immune response was comparable.

###### **IM101063**

Study IM101063, a double-blind, randomized, placebo-controlled, parallel-group, multiple-dose study in subjects with active RA who are on background DMARDs (MTX or MTX plus no more than 1 additional oral DMARD) was designed to evaluate the safety and immunogenicity of several doses of SC abatacept. No deaths were recorded during the short-term 12-week phase of the study. Safety evaluations from the 51 abatacept-treated subjects and 17 placebo-treated subjects showed that abatacept administered by SC injections weekly was safe and well tolerated. The most common infections observed in both abatacept-treated and placebo-treated subjects were upper respiratory and urinary tract infections. There were 7 SAEs (diastolic dysfunction/chest discomfort/dyspnea/COPD/sleep apnea in 1 subject; wound infection in 1 subject; and drug overdose in 1 subject) reported during the short-term phase of the study. All the SAEs were reported to be unrelated or unlikely related to study drug by the investigator. In addition, injection site reactions from the weekly SC injections were uncommon and predominantly mild in intensity. Overall, the safety profile for SC abatacept was observed to be consistent with that for IV abatacept.

### **IM101173**

IM101173, a multi-center open-label study in adults with active RA requiring a new therapeutic intervention, was designed to evaluate SC abatacept in a monotherapy setting and to assess if the use of background MTX influences the development of immunogenicity. An initial IV abatacept loading dose was not given in this study in order to maximize the potential for immunogenicity following SC administration of abatacept. In addition, this study was designed to assess whether the development of immunogenicity following SC abatacept impacted the PK, safety, or effectiveness of the drug. Safety and exploratory efficacy data for subjects treated for 4 months with SC abatacept in Study IM101173 were available.

A total of 100 subjects with RA and requiring a new therapeutic intervention were stratified based on their current MTX use to 4 months of open-label treatment with SC abatacept monotherapy (N = 49) or to SC abatacept in combination with MTX (N = 51). Subjects in both cohorts received weekly SC injections of abatacept 125 mg (dosing irrespective of body weight).

The safety profile for SC abatacept in adults with RA in this study appeared favorable overall. Treatment with SC abatacept 125 mg/week, with or without background MTX, and in the absence of an IV loading dose, was well tolerated by subjects with RA in this study. During the 4-month short-term treatment period, there were no deaths, SAEs assessed as at least possibly related to study treatment were reported in only 2 subjects, and AEs resulted in treatment discontinuation for 4 (4%) subjects. Local injection site reactions, a common finding for SC-injected drugs, were infrequent (7%); all were mild and did not result in treatment discontinuation. Similarly, systemic injection site reactions occurring within 24 hours following SC injection of abatacept were also infrequent (8%) and mostly mild in intensity. One subject experienced angioedema following the initial SC injection of abatacept, which was moderate in intensity, serious and led to treatment discontinuation. The angioedema resolved the same day. The rate of systemic injection reactions with SC abatacept was consistent with the rates of peri-infusional AEs reported for IV abatacept.

### **STUDY IN SYSTEMIC LUPUS ERYTHEMATOSUS**

In NCT 001 10678, A phase IIb study in SLE was conducted and published. 118 patients were treated with 10mg/kg abatacept i.v. in the standard RA dose, and 57 with placebo. 65% completed 12 months of study. The primary outcome, rate of flare beginning after prednisone taper, over a total of 12 months, measured by adjudicated BILAG A and B, did not show significant differences between the groups. However, patients with lupus polyarthritis at entry had significantly fewer flares compared to placebo in both BILAG A flare (36.5% in placebo vs 12.5% in abatacept) and physician-identified flares. The incidence of serious adverse events was higher in abatacept (19.8%) vs placebo (6.8%) without any particular type of SAE identified.

In a recent study in patients with lupus nephritis, 198 individuals were treated with abatacept i.v.. for 12 months (one group with a loading dose of 30 mg/kg once a month x3 followed by 10 mg/kg monthly; a second with 10 mg/kg monthly i.v. for the entire 12 month period). At 12 months, there were no statistically significant differences in response rates (defined as complete renal response or partial- plus- complete renal responses) between the group that received placebo infusions plus standard care compared to either of the groups that received abatacept plus standard care. The occurrence of severe adverse events did not differ significantly between the groups: SAEs occurred in 28-33.3% of the abatacept groups and 31% of the placebo group. There were 7 deaths in the abatacept groups (one of which was a gunshot wound) for a rate of 2.5%, with 7 deaths in the placebo group for a rate of 7%. Treatment related SAEs occurred in 19-20% of the abatacept groups and 15% of the placebo groups.

To summarize, there are published data on abatacept, administered i.v., to 316 patients with SLE for 12 months. In the patients most comparable to the subjects to be studied here (no active nephritis or CNS disease), SAEs occurred in approximately 20%. We expect the SAE rate to be lower in the study proposed here because the treatment duration is 16 weeks rather than 52 weeks. Another difference is that the treatments will be administered subcutaneously instead of intravenously. Perhaps more relevant to this proposal is study IM101173 described above, in which patients with rheumatoid arthritis on methotrexate received 125 mg of abatacept weekly for 16 weeks; SAEs in that study occurred in 2%. One individual had pneumocystis pneumonia requiring hospitalization.

### **SC formulation in pediatric population**

Data are not available for the safety of SC abatacept in the pediatric population.

## **1.4 Overall Risk/Benefit Assessment**

Lupus is an autoimmune disorder that involves inflammatory polyarthritis that can lead to deformity, significant physical disability, and poor quality of life.

In the past decade, the success of abatacept and other biologic immune/inflammation modifiers such as TNF inhibitors in suppressing rheumatoid arthritis have led to testing of some of these products in patients with SLE. To date, TNFalpha inhibitors have been disappointing in that a high infection rate has caused early stopping of some trials. Although the efficacy, tolerability, and safety profile of abatacept was demonstrated in the RA clinical development program, the two trials to date using abatacept in SLE did not identify an overall benefit. However, the subset of patients with active lupus polyarthritis at entry had significant benefit, shown as a significant reduction in flares of SLE. Abatacept, a biologic DMARD with a unique mechanism of action, has demonstrated a good efficacy/safety profile in RA. Abatacept has been on the market in the US since January 2006 and in Europe since May 2007.

Abatacept, a selective costimulation modulator, is a soluble fusion protein that consists of the extracellular domain of human cytotoxic T-lymphocyte (T-cell)-associated antigen 4 (CTLA-4) linked to the modified Fc (hinge, CH2, and CH3 domains) portion of human immunoglobulin G1 (IgG1). An intravenous (IV) formulation of abatacept is approved in several countries including the United States and in the European Union (EU) for the treatment of moderate to severe rheumatoid arthritis (RA) in adults. The subcutaneous preparation is currently approved in the United States for rheumatoid arthritis in adults. Based on the clinical trial experience in adults, the risks that may be associated with the use of abatacept include infections, some of which may be serious or fatal, infusion related reactions, and an increase in respiratory adverse events and infections in patients with chronic pulmonary obstructive disease (COPD). Other potential risks may include the development of malignancies or autoimmune disorders, but an increased risk of these types of events has not been observed. As with the use of any protein therapeutic, antibodies against abatacept (immunogenicity) may develop. The rate of immunogenicity has generally been low and there has not been an apparent effect on safety, efficacy, or pharmacokinetics (PK). Abatacept intravenous is also currently approved for the treatment of moderately to severely active polyarticular juvenile idiopathic arthritis (JIA) in pediatric patients 6 years of age or older in several countries including the USA for patients aged 6 - 17 years old. Abatacept was generally safe and well tolerated in subjects with JIA.

For the period from the fourth quarter of 2005 to the third quarter of 2009 inclusive, the total number of patients exposed to abatacept is estimated to be equivalent to 60,225 patient-years of exposure. The overall pattern of safety reporting raises no new safety concerns. A subcutaneous (SC) formulation of abatacept is being studied for the treatment of a number of immune mediated disorders; results from 3 completed clinical studies in RA are included in this document.

### **1.5 Study Rationale**

SLE is a systemic autoimmune disease with life-threatening manifestations. Currently, there are limited approved treatments for SLE and none (except high dose glucocorticoids) have been shown to prolong survival or permanently reverse the course of the disease. SLE remains a disease with unmet medical need, especially for patients with active and life-threatening manifestations, and for the many with adverse effects from chronic glucocorticoid use.

Lupus arthritis is a common manifestation of lupus. It can cause a debilitating and disabling condition in lupus patients resulting in poor quality of life. Currently, the therapies in treating lupus arthritis such as glucocorticoids, NSAIDs, hydroxychloroquine, belimumab or MMF are far from optimum, inducing complete remission in fewer than 50% of affected patients.

Thus, there is an unmet need in patients with lupus arthritis for more effective and safe therapy. Rationale for abatacept to work in treating lupus arthritis is based on abatacept's mechanism of action, evidence of its safety in lupus nephritis patients and experience in Rheumatoid arthritis.

## **2 STUDY OBJECTIVES**

### **2.1 Primary Objective**

Improvement of lupus inflammatory polyarthritis measured by proportion of patients who achieve >=20% improvement in tender and swollen 28 joint counts at 16 weeks.

#### **Secondary Objectives:**

1. Mean and median joint scores in treated vs placebo patients at 16 weeks, compared to baseline scores.
2. Proportion of patients who achieve improvement in SLEDAI 2K at 16 weeks of >3 points, comparing abatacept to placebo.
3. Proportions of patient who do not worsen by PGA score ( $\leq 0.8$  change from initial PGA score on 3 point line).
4. Mean and median changes in CDAI comparing abatacept to controls at 8, 12 and 16 weeks.

5. Changes in a) synovitis, b) tenosynovitis and c) erosions measured by high-energy ultrasound with Doppler flow at zero, and 16 weeks, compared to placebo.
6. Steroid sparing effect of abatacept, measured as ability to taper prednisone to <10mg/day by week 16 comparing abatacept-treated subjects to placebo-treated subjects.
7. Change in fatigue from baseline to 16 weeks as measured by the FACIT fatigue score instrument
8. Change in quality of life comparing baseline to 16 weeks as measured by the SF 36.
9. Safety, measured in standard methods as AE and SAE, including likelihood that the AE/SAE was related to the study biologic.
10. Time to response, measured as joint counts (sum of tender and swollen joints) at zero, 4, 8, 12, and 16 weeks.
11. Change in peripheral blood T cell compartments indicating decline in pro-inflammatory profiles, i.e., we expect decrease in CD4+ effector T cells that make IFNgamma (TH1) and IL-17 (TH17) and increase in ratio of Treg to Teff, as well as decreased function of Thelper and increased functions of Tregs. CD4+CD25+ Foxp3+ and CD8+Foxp3+ will be the definition of regulatory T cells. These will be measured at baseline and 16 weeks
12. Change in anti-DNA and total IgG levels, as well as rise in serum complement levels as disease improves and fewer B cells are activated: measure these at zero, 8 and 16 weeks.
13. Effects of abatacept on serum levels of BLyS (BAFF). As numbers of activated B cells and plasmablasts fall, we expect an increase in BLyS levels. Measure at baseline and 16 weeks.
14. Changes in transcriptome in whole blood and/or purified mononuclear cells in peripheral blood, and changes in interferon-induced gene expressions at baseline that may predict response or non-response at 16 weeks. Measure at baseline and last study visit.

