Study Objectives:	
Primary: Improvement of lupus inflammatory polyarthrits measured by <math>\geq 20\%</math> improvement in tender and swollen 28 joint counts at 16 weeks.
 
Secondary:
 
 
1. Mean and median joint counts in treated vs placebo patients at 16 weeks, compared to baseline scores.
 
2. Proportion of patients who achieve improvement in SLEDAI 2K at 16 weeks of <math>>3</math> points.
 
3. Mean and median changes in CDAI comparing abatacept to controls at 16 weeks.
 
4. Changes in a) synovitis, b) tenosynovitis and c) erosions measured by high-energy ultrasound with Doppler flow at zero and 16 weeks.
 
5. Proportion of patients with BILAG A in any system other than musculoskeletal at week 16.
 
6. Proportion of patients with no significant increase in physician global assessment (defined as <math><0.8</math> on a 1-10 scale) at 16 weeks.
 
7. Steroid sparing effect of abatacept, measured as ability to taper prednisone to <math>\leq 10</math>mg/day by week 16.
 
8. Effects on fatigue at 16 weeks as measured by the FACIT fatigue score instrument
 
9. Effects on quality of life at 16 weeks as measured by the SF 36
 
10. Safety, measured in standard methods as AE and SAE, including likelihood that the AE/SAE was related to the study biologic.
 
11. Time to response, measured as time to <math>\geq 20\%</math> decrease in joint counts (sum of tender and swollen joints) at zero, 4, 8, 12, and 16 weeks.
 
12. Change in peripheral blood T cell compartments indicating decline in pro-inflammatory profiles, i.e., we expect decrease in CD4+ effector T cells that make IFNgamma (TH1) and IL-17 (TH17) and increase in ratio of Treg to Teff, as well as decreased function of Thelper and increased functions of Tregs. CD4+CD25+ Foxp3+ and CD8+Foxp3+ will be the definition of regulatory T cells. These will be measured at zero and 16 weeks.
 
13. Change in anti-DNA and total IgG levels, as well as rise in serum complement levels as disease improves and fewer B cells are activated: measure these at zero, 8 and 16 weeks.
 
14. Effects of abatacept on serum levels of BLyS (BAFF) at baseline, 8 and 16 weeks. As numbers of activated B cells and plasmablasts fall, we expect an increase in BLyS levels
 

--------------------------	---

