Inclusion Criteria	
 
1. Meet at least 4 of the 11 American College of Rheumatology (ACR) 1997 criteria for classification of SLE (see Appendix 1). OR meet the recent classification recommended by SLICC (Appendix 2)
 
2. <math>\geq 3</math> swollen and tender joints on 2 examinations at least 2 weeks apart and no more than 8 weeks apart.
 
3. SLEDAI2K score <math>\geq 4</math> indicating active disease.
 
4. Documented positive ANA (<math>\geq 1:80</math>) and/or anti-dsDNA during course of SLE.
 
5. Men and women, at least 18 years of age. Women of childbearing potential must use adequate method(s) of contraception to avoid pregnancy throughout the study and for up to 2 months after last study drug dose. They must have a negative serum or urine pregnancy test prior to the start of study medication.
 
6. Background therapies allowed: antimalarials (dose constant for <math>\geq</math> one month before study entry and during 16 weeks of trial), methotrexate (same criteria as for antimalarials), azathioprine (same criteria), mycophenolate (same criteria), leflunomide (same criteria). During the screening period and for up to 6 weeks after randomization, a daily prednisone (or equivalent) regimen of up to 20 mg daily may be initiated to treat the moderate to severe disease activity present at screening. The initial steroid regimen is not required if investigators or patients believe that the risks would outweigh the potential benefits. Patients who do not take any glucocorticoids during the study will be included in the treatment groups and analysis.
 
 
*Steroids should be tapered to a target dose of no more than 10 mg/day of prednisone (or equivalent) by the end of Week 8 (Day 56). The steroid regimen should be tapered as quickly as safely possible. Prednisone dose requirements higher than 10 mg daily at the 8 week visit will cause the patient to be ruled a non-responder for the abatacept treatment arm.

---------------------------	--

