#### **6.4.2 Secondary Efficacy Assessments**

1. Changes in synovitis, tenosynovitis and erosions measured by high-energy ultrasound with Doppler flow at Baseline and 16 weeks.
2. **STEROID SPARING EFFECT OF ABATACEPT, MEASURED AS COMPARISON OF DAILY DOSE AT BASELINE AND 16 WEEKS AND AS CUMULATIVE GLUCOCORTICOID DOSE OVER THE 16 WEEKS PERIOD.**
3. **PROPORTION OF SUBJECTS WITH NO BILAG A IN ANY SYSTEM OTHER THAN MUSCULOSKELETAL AT 16 WEEKS.**
4. Proportion of subjects with no deterioration in physician global assessment at 16 weeks.
5. Comparison of fatigue at baseline and 16 weeks as measured by the FACIT
6. Comparison of quality of life at baseline and 16 weeks as measured by the SF 36
7. Safety, measured in standard methods as AE and SAE, inducing likelihood that the AE/SAE was related to the study biologic.
8. Time to  $\geq 20\%$  response, measured as joint counts (sum of tender and swollen joints) at baseline, 4, 8, 12 and 16 weeks.
9. Change in peripheral blood T cell compartments indicating decline in pro-inflammatory profiles, i.e. we expect decrease in CD4+ effector T cells that make IFNgamma (TH1) and IL-17 (TH17) and increase in ratio of Treg to Teff, as well as increased functions of the Tregs and decreased function of the helper T cells. CD4+CD25+ Foxp3 and CD8+Foxp3+ will be the definition of regulatory T cells. These will be measured at baseline and 16 weeks.
10. Change in anti-DNA and complement levels measured at zero, 8 and 16 weeks.

11. Change in BLyS levels from baseline to 16 weeks. We expect BLyS levels may rise as abatacept interferes with T cell action and thus with T cell help to B cells, with less B cell activation and less progression of B cells to short-lived plasma cells, and therefore a potential drop in B cell numbers and rise in BLyS levels. If this does not occur, then the effects of abatacept on B cells would be considered less dramatic than the effects of B cell depletion by rituximab.
12. Effects of treatment on extra-articular systems involved with SLE, such as skin, mucous membranes, serosal surfaces, systemic symptoms at baseline, 4, 8, 12 and 16 weeks.

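### The steroid-sparing proportion has two conflicting cut-offs and no stated denominator, so it is diluted and hard to read as steroid sparing

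*Combined protocol and SAP*

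**What the plan says.** The protocol describes steroid sparing in three places, in three ways.

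- Section 2, secondary objective 6: "measured as ability to taper prednisone to <10mg/day by week 16", with the abatacept arm compared to the placebo arm.
- Synopsis, secondary objective 7: "Steroid sparing effect of abatacept, measured as ability to taper prednisone to" 10 mg/day or less by week 16.
- Section 6.4.2, item 2: "MEASURED AS COMPARISON OF DAILY DOSE AT BASELINE AND 16 WEEKS AND AS CUMULATIVE GLUCOCORTICOID DOSE OVER THE 16 WEEKS PERIOD".

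No passage says which of these governs. The first two name no denominator and no minimum starting dose.

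The entry rules set an upper limit on prednisone (Synopsis exclusion 11; Section 4.2.1, prohibited treatments) but no lower one. Steroids are optional: "The initial steroid regimen is not required if investigators or patients believe that the risks would outweigh the potential benefits". The Synopsis adds: "Patients who do not take any glucocorticoids during the study will be included in the treatment groups and analysis".

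Both arms follow the same taper: "Steroids should be tapered to a target dose of no more than 10 mg/day of prednisone (or equivalent) by the end of Week 8". Section 5.5.1 does not permit more than 10 mg/day after week 8. Section 4.1 regards patients who need more than 10 mg at or after the week-8 visit as treatment failures; the Synopsis rules those above 10 mg at that visit non-responders.

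Section 8.4.3 plans Fisher's exact test for proportions, Wilcoxon rank sum tests for quantitative outcomes, and linear regression for continuous outcomes.

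**The concern.** A measure of steroid sparing should separate patients who could reduce their dose because of treatment from those who had nothing to reduce. This proportion does not do so.

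Read as a threshold, it lets a patient who enters on 0, 5 or 7.5 mg and stays there succeed without any taper. A patient who enters above 10 mg is instructed, in either arm, to be at or below 10 mg eight weeks before the endpoint is read. Both features raise the success rate in both arms and compress the difference between them. A finding of no difference would then say little about steroid sparing, and a high success rate could be misreported as evidence of it.

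The cut-off conflict is a separate problem. It falls exactly on the dose that the taper rule names as its target, where patients who follow the rule may well cluster.

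**Working it through.** **The plan's own figure.** The documents give no rate, sample size or power for this endpoint. The only sample-size figure is for joint response (Section 8.1): 67% versus 30%, 0.05, power 0.8, 28 per group. The two-sided pooled formula without continuity correction reproduces it:

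n = [1.96 × √(2 × 0.485 × 0.515) + 0.8416 × √(0.67 × 0.33 + 0.30 × 0.70)]² / 0.37² = (1.385 + 0.553)² / 0.1369 ≈ 27.4, rounded up to 28.

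With 12% dropout, 28 / 0.88 = 31.8, rounded up to 32. This supplies the 28 completers per arm used below; it does not bear on steroid sparing itself.

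**Effect of the cut-off.** Take a patient who tapers from 20 mg to 10 mg by week 8 and is on 10 mg at week 16. The Synopsis counts a success and Section 2 a failure. With 28 per arm, each such patient moves that arm's rate by 1/28 = 3.6 points.

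**Dilution.** Let f be the share of each arm at or below the cut-off at entry. The documents do not give f. Assume that these patients all stay there and count as successes, and that the others succeed at 70% (abatacept) versus 40% (placebo), also assumed. Then:

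observed rate = f + (1 − f) × rate among the others

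observed difference = (1 − f) × 30 points

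| f | Abatacept | Placebo | Difference (points) | Fisher power, 28 per arm, two-sided 0.05 |
|---|---|---|---|---|
| 0 | 70% | 40% | 30 | 0.51 |
| 0.3 | 79% | 58% | 21 | 0.31 |
| 0.5 | 85% | 70% | 15 | 0.17 |
| 0.8 | 94% | 88% | 6 | 0.03 |

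Borrowing the joint-response rates (67% versus 30%) instead gives the same pattern. At f = 0, 0.25, 0.5 and 0.75 the difference is 37, 27.8, 18.5 and 9.3 points, and power is 0.71, 0.47, 0.25 and 0.07.

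**Relaxing the assumption.** Low-dose entrants need not stay put: the Synopsis lets prednisone up to 20 mg be started until 6 weeks after randomization, and Section 4.2.3 allows a rescue increase. Suppose 90% of them succeed on abatacept and 70% on placebo (assumed), a 20-point difference. The observed difference is then f × 20 + (1 − f) × 30:

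- f = 0.3: 6 + 21 = 27 points
- f = 0.5: 10 + 15 = 25 points
- f = 0.8: 16 + 6 = 22 points

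So the loss ranges from slight to severe, depending on f and on what low-dose entrants do, and the documents settle neither.

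**The case against.** A reader might infer that the endpoint cannot show a steroid-sparing effect at all, because success is already secured at entry for some patients and forced on the rest by week 8. The documents do not support that, for four reasons.

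- The week-8 rule is a target with a stated consequence. Patients who still need more than 10 mg are classed as failures, and exceeding the limit is not among the mandatory withdrawal reasons in Sections 4.2.3 and 4.4. Their number can differ by arm. This stands.
- Under the Section 2 cut-off, a patient on exactly 10 mg obeys the week-8 rule and still fails, so that version is not forced by the rule. This stands.
- Counting steroid-free patients as successes is an inference. The Synopsis keeps them in the analysis but does not say how they score on ability to taper. This also stands, although the silence is itself a gap to close.
- Cumulative dose is already listed in Section 6.4.2, so a better measure exists. True, but the stated objectives in Section 2 and the Synopsis use the threshold, and nothing gives cumulative dose precedence.

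It is also tempting to discard the change in daily dose from baseline to week 16, because its sign depends on when prednisone was started. A patient who goes from 20 mg at baseline to 10 mg scores −10. One who is on none at baseline, starts 20 mg at week 2 and tapers to 10 mg scores +10. But +10 correctly records more steroid than at entry, and the timing rules apply to both randomized arms, so this is no reason to drop the measure.

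Finally, this is one of 14 secondary objectives in a 64-patient trial sized for joint response only. That limits the consequence; it does not remove the inconsistency.

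**Conclusion.** The concern holds as a matter of definition and sensitivity. The two cut-offs conflict at the taper target, the denominator is unstated, and patients with nothing to taper are mixed with those who have. The proportion is insensitive and difficult to interpret as steroid sparing. It is not incapable of showing a difference, since patients can exceed the limit and fail.

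The size is conditional. The fall from 30 points to 21, 15 or 6 assumes that everyone at or below the cut-off at entry stays there and counts as a success. With the alternative assumption shown, the difference falls only to 27, 25 or 22. The 70%, 40%, 90% and 20-point-type inputs are illustrations, not figures from the plan. The definition should be corrected, but the point does not touch the primary endpoint.

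**What to change.** 1. In Section 2, objective 6, and Synopsis objective 7, name cumulative glucocorticoid dose from day 1 to week 16 as the main steroid-sparing measure for all patients. Compare it between arms with adjustment for the prednisone dose at the baseline visit; the regression provision in Section 8.4.3 can carry this.
2. Report the taper proportion only among patients above the cut-off at the baseline visit, a group fixed before treatment. Patients who start prednisone later are captured by the cumulative dose.
3. Use one analysis cut-off throughout.
4. Keep the change in daily dose from baseline to week 16 as supportive.

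The cost is wording. Concomitant medication is already reviewed at every visit, and Section 6.4.2 already presupposes enough dose detail to compute a cumulative total. The restricted proportion rests on fewer patients: at f = 0.5, 28 × 0.5 = 14 per arm. It therefore gains in interpretation, not necessarily in power, which is why it should not be the main measure.

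Separately, the sponsor must reconcile the steroid passages, because steroid exposure is the outcome here. The Synopsis, Section 4.1, Section 4.2.3, Section 4.3.1 and Section 5.5.1 differ on the upper limit (20 or 30 mg), on the period in which higher doses are allowed (up to 4 or up to 6 weeks), and on whether prednisone is tapered or continued at the baseline dosage. No dose or clinical rule is proposed here.
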